9.3.3	Visit 3: Baseline with Avaira Toric & Dispense of Avaira Vitality Toric lenses.....	19
9.3.4	Visit 4: 2-week follow up for Avaira Vitality Toric	21
9.3.5	Visit 5: 1-month follow up on Avaira Vitality Toric Lenses & Study Exit	22

10	Adverse Events and their Reporting	24
10.1	Adverse Response Definitions	24
10.2	Procedures for Adverse Events	26
10.3	Reporting Adverse Events	27
10.4	Discontinuation from the Study	27
11	Statistical Analysis	27
11.1	Statistical analysis	27
12	Data Quality Assurance	28
12.1	Study monitoring	28
12.2	Record keeping	28
12.3	Record retention	28
12.4	Data Entry / Data Management	28
12.5	Confidentiality	29
12.6	Publication	29
13	Study Costs and Subject Compensation	29

1 Introduction

The utilization of soft toric contact lenses has increased significantly over the past few years. CooperVision (CV) produces a number of toric contact lens products including the Avaira toric brand (Enfilcon A) and Avaira Vitality brand (Fanfilcon A). All Enfilcon A toric lenses and Fanfilcon A toric lenses feature CooperVision's exclusive Aquaform® Technology and PEG (Polyethylene Glycol). This combination of material technologies provides a contact lens with high oxygen permeability that is naturally wettable and offers unique comfortable experience.

This study is designed to evaluate how adapted contact lens wearers of Enfilcon A toric lenses will perform following a refit with Fanfilcon A toric lenses, a novel soft contact lens with optimized lens geometry and enhanced water content and UV protection, over one month of daily wear. Overall lens wear experience, including visual quality, lens fit and subjective responses will be assessed.

2 Study Objective

The aim of this study is to determine if adapted contact lens wearers of Enfilcon A toric lenses can be confidently refit into Fanfilcon A toric lenses and be successful after at least one month of daily wear.

Primary outcomes:

- High contrast distance visual acuity (Snellen) with contact lenses
- Lens fit performance (centration, corneal coverage, post blink movement)
- Investigator's fit acceptability

3 Study Hypothesis

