– Overall fit acceptance (0 - 4) and reason if Grade 2 or less.

- [REDACTED]
[REDACTED]
[REDACTED]
[REDACTED]
[REDACTED]
[REDACTED]

- To be successfully dispensed, subjects must show >Grade 2 lens fit acceptance with the trial fit lens and must be correctable to 20/30 (0.18 logMAR) or better in each eye with the study contact lenses.
- If the lenses are not a suitable fit to be dispensed then the subject will be discontinued and an Exit Form (App 13) will be completed.
- The subject will be instructed to wear the lenses on a daily wear basis, (at least 5 days/week, >8 hours/day), until Visit 4 appointment, unless they experience a problem which warrants lens removal.
- The Investigator or a clinical assistant will review instructions and warnings for lens wear and care, when to remove lenses, and other important issues with the subject.
- Subjects, who appear unable or unwilling to follow instructions to a degree that, in the Investigator's opinion, jeopardizes the subject's wellbeing or the validity of the study, will be discontinued. The reason for discontinuation will be documented.
- The subject will be discharged and asked to return for a follow-up visit (V4) after 2-weeks

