11.1 Statistical analysis

Descriptive statistics will be provided on information regarding baseline variables (e.g., age, gender). Differences between lenses and over time will be compared using Paired t-tests. Paired t-tests

/analysis of variance for normal (interval/continuous) data. The appropriate test will be selected based on tests of normality. Means and standard deviations will be provided for each variable.

A Binomial test will be used to analyze the results for the count data of subjective preferences. The number of "no preference" will be evenly distributed to the two options on the basis they would be equally likely to choose either. All subjects who were evaluated will be used in the analysis. In the event of missing data, individual data points will be excluded in the analysis and not extrapolated from the collected data.

12 Data Quality Assurance

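### The aim is whether wearers can be refit and succeed at one month, but the 1-month results cover only subjects who passed the Visit 3b fit and acuity gate, and no visible analysis estimates refit success.

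*Combined protocol and SAP*

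**What the plan says.** Section 2 gives the aim as finding out whether Enfilcon A toric wearers "can be confidently refit into Fanfilcon A toric lenses and be successful after at least one month of daily wear". The primary outcomes listed there are Snellen acuity with the lenses, lens fit performance and "Investigator's fit acceptability".

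The test lens is first tried at Visit 3b (Section 9.3.3). After 10-15 minutes of settling, acuity and lens fit are recorded, including "Overall fit acceptance (0 - 4) and reason if Grade 2 or less". The dispensing condition follows: "subjects must show >Grade 2 lens fit acceptance with the trial fit lens and must be correctable to 20/30", with the acuity limit applying to each eye. The consequence of not meeting it is also stated: "If the lenses are not a suitable fit to be dispensed then the subject will be discontinued". An Exit Form is then completed.

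Section 11.1 says "Differences between lenses and over time will be compared using Paired t-tests", with analysis of variance as an alternative, and "Means and standard deviations will be provided for each variable". A binomial test is planned for subjective preferences only. On the analysis set it says "All subjects who were evaluated will be used in the analysis", and it then says that missing data points are excluded rather than filled in.

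The inclusion criteria in Section 9.1 require a successful fit, and 20/30 or better in each eye, with the study lenses. Table 1 (Section 9.2.1) lists both the control and the test lens under that name. The eligibility checklist is completed at Visit 1 (Section 9.3.1).

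**The concern.** Whether wearers can be refit and succeed is a question about a proportion: of those in whom the test lens was tried, how many were wearing it successfully a month later? A subject whose fit or acuity is inadequate at Visit 3b is direct evidence on that question, and the evidence is unfavourable. Under the plan this subject leaves before Visits 4 and 5, contributes nothing to the 1-month comparison, and is not counted as a failure in any visible analysis.

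The selection acts on fit acceptance and acuity, which are also primary-outcome domains. Good 1-month fit and acuity could therefore be read as an answer to the study's aim when they describe only subjects in whom the initial refit had already worked.

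The eligibility wording adds an ambiguity. Because the criteria refer to study lenses without saying which, a Visit 3b failure could be treated either as a failed refit or as a subject found not to have been eligible. The documents do not say which.

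**Working it through.** **What happens to a subject who fails at Visit 3b**

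1. Visit 3a (control lens): acuity and fit recorded.
2. Visit 3b (test lens): acuity and fit recorded; the gate is listed after these assessments.
3. Gate failed: discontinued, Exit Form completed, no Visit 4 or Visit 5.
4. Paired comparison of Visit 3a with Visit 5: no Visit 5 value, so no pair, and the missing point is excluded under Section 11.1.
5. Visit 3b summaries: the values exist and can be used, since all evaluated subjects are included.
6. Refit success: Section 11.1 states no criterion, proportion, denominator or failure rule.

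The gap is therefore at steps 4 and 6. It follows from the text and does not depend on any assumed rate.

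**The plan's own figure**

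Section 5.1 gives 44 subjects for SD 2.4, alpha 0.05, power 0.8 and a difference of 1.04. For a two-sided paired t-test the exact (noncentral t) power at n = 44 is 0.802, and the detectable difference at power 0.8 is 1.037. The figure reproduces. It concerns comfort, not refit success, and is not in dispute here.

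**Illustration of the size**

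The documents give no failure rate. Assume that 48 subjects have the test lens tried at Visit 3b, that k are not dispensed, and that all others succeed.

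- Of those tried: (48 - k)/48.
- Of those dispensed: (48 - k)/(48 - k) = 100% for every k.
- Exact (Clopper-Pearson) 95% limits for x successes in n: lower = Beta quantile 0.025 with parameters (x, n - x + 1); upper = Beta quantile 0.975 with parameters (x + 1, n - x). When x = n, the lower limit is 0.025^(1/n) and the upper limit is 100%.

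| k (assumed) | Of those tried (95% CI) | Of those dispensed (95% CI) |
|---|---|---|
| 0 | 48/48 = 100% (92.6-100) | 48/48 = 100% (92.6-100) |
| 1 | 47/48 = 97.9% (88.9-99.9) | 47/47 = 100% (92.5-100) |
| 2 | 46/48 = 95.8% (85.7-99.5) | 46/46 = 100% (92.3-100) |
| 4 | 44/48 = 91.7% (80.0-97.7) | 44/44 = 100% (92.0-100) |
| 8 | 40/48 = 83.3% (69.8-92.5) | 40/40 = 100% (91.2-100) |

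The row k = 4 matches the gap between 48 and 44 in Section 5.1, but that section does not divide its allowance by cause, so k = 4 remains an assumption. With k = 0 the two columns agree.

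**The case against.** The strongest reply is that conditioning on a successful fit is the design. Section 9.1 limits the population to people who can be fit with the study lenses, Section 3.1 states the hypothesis as a difference in lens performance, and a lens that was never dispensed cannot have 1-month wear data. All of this is true, and it makes the paired comparison a legitimate conditional one. It does not answer the aim in Section 2, which is framed as whether wearers can be refit and be successful.

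A second reply is that the information is not lost. Visit 3b values are recorded before the gate, exit reasons are documented (Sections 9.1, 9.3.5 and 10.4), and comparing Visit 3a with Visit 3b falls within comparisons between lenses. This also stands, and it makes the fix cheap. But that pair is not named; it sets a lens worn for at least 2 hours that day against one settled for 10-15 minutes, and it says nothing about one month. Recording exits is not a commitment to tabulate them over a stated denominator.

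A third reply is redaction. The synopsis row after the primary endpoints and parts of the Visit 3b to Visit 5 text are blacked out, so a success endpoint could sit there. Section 11.1 shows no redaction. The point is therefore limited to the visible text and held with moderate confidence.

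A reader might infer more than the documents support:

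- *That failures are removed from every analysis.* The mention in Section 9.1 of subjects successfully completing the study is a recruitment target. The pre-export cohort discussion in Section 12.1 centres on protocol deviations and adverse events, and a non-dispense under the protocol's own rule is not in itself either. Section 11.1 keeps all evaluated subjects.
- *That the planned paired test would show a spurious gain in fit grade from Visit 3b to Visit 5 as failures leave.* A subject without Visit 5 forms no such pair. Only descriptive means with different numbers of subjects could shift, and a subject who fails on acuity alone need not have a low fit grade.
- *That the plan would report 100% success.* It reports no success proportion at all.

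**Conclusion.** The concern holds on the visible text and should be fixed. The plan, followed as written, gives 1-month results only for subjects who passed a gate on primary-outcome domains, and no visible analysis estimates refit success or counts a non-dispense as a failure. Whether a Visit 3b failure is a failed refit or an ineligible subject is left open by the study-lens inclusion criteria.

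The size is unknown, and it is zero if nobody fails at Visit 3b. The contrast between 91.7% and 100% is between the proposed statistic and its conditional counterpart. It rests on three assumptions: 48 tried, 4 not dispensed, and every other subject successful. The paired comparisons remain usable if they are labelled for what they are.

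**What to change.** In Section 11.1:

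1. Report the proportion of subjects successful at Visit 5, with an exact 95% CI, over all subjects in whom the test lens was tried at Visit 3b. State the fit and acuity criterion for success in advance; the investigator who grades fit is not masked (Section 9.2.7), which is a further reason to do so. Count Visit 3b non-dispenses and lens-related discontinuations before Visit 5 as failures, with numbers and reasons. Show exits unrelated to the lens separately, with a sensitivity analysis that counts them as failures.
2. Label the Visit 4 and Visit 5 comparisons as conditional on dispensing.
3. State that a subject who fails at Visit 3b is not removed from the analysis as ineligible under the study-lens criteria in Section 9.1.

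The cost is wording plus one table from data already collected at Visits 3b and 5 and on the Exit Form. No visits or subjects are added. The reported figure may be less favourable.

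As a separate point, the fit condition at Visit 3b reads as strictly above Grade 2, while the inclusion criteria and Visit 2 read as Grade 2 or above. The symbol may have been altered when the text was extracted. It should be checked against the source document and the passages reconciled, since the condition determines who is not dispensed.

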9.3.4 Visit 4: 2-week follow up for Avaira Vitality Toric

The 2-week follow-up visit for Avaira Vitality Toric lenses will be scheduled 14 ± 2 days after Visit 3. The subject should wear the lenses for a minimum of 2 hours prior to the appointment. If the subject attends without lenses or with less than 2 hours of lens wear on that day and they are not having any problems with their lenses, the visit should be rescheduled, if possible within the visit window.

The following clinical test variables will be recorded on the CRFs as indicated:

- Confirm if any changes to health or medications (App 10)
- [REDACTED]
[REDACTED]
[REDACTED]

Visit 5a: 1-month follow-up for Avaira Vitality Lenses

The following variables will be recorded on the CRFs as indicated:

- Confirm if any changes to health or medications (App 12)
- [REDACTED]
 - [REDACTED]
 - [REDACTED]
 - [REDACTED]
- [REDACTED]
 - [REDACTED]
 - [REDACTED]
 - [REDACTED]
- Vision
 - High contrast distance monocular Snellen visual acuity
 - High contrast distance binocular Snellen visual acuity
- [REDACTED]
 - [REDACTED]
 - [REDACTED]
- Lens fit
 - Lens centration (centered/slightly decentered/substantially decentered)
 - Corneal coverage [Y/N]
 - [REDACTED]
 - Post-blink movement (0-4 Likert scale)
 - [REDACTED]
 - [REDACTED]
 - [REDACTED]
 - [REDACTED]
 - [REDACTED]
 - Overall fit acceptance (0 - 4) and reason if Grade 2 or less.
- [REDACTED]
 - [REDACTED]
 - [REDACTED]
 - [REDACTED]
 - [REDACTED]
 - [REDACTED]
 - [REDACTED]
 - [REDACTED]
 - [REDACTED]
- Vision

- High contrast distance monocular Snellen visual acuity
- High contrast distance binocular Snellen visual acuity

- [REDACTED]
- [REDACTED]
- Remove study lenses and perform slit lamp examination.
- Exit subject from the study, see details below.

Visit 5b: Study Exit

- The Study Exit Form (App 13) must be completed when a subject exits the study. This will occur either at study completion, i.e. at Visit 5, or if the subject is discontinued from the study at another time. If there are records entered into the clinic's own patient chart system the exit date should also be recorded on these source documents.
- A Study Exit Form must be completed for all subjects who have taken a study ID number. Post-study follow-up visits will be scheduled if the Investigator judges this is necessary.
- At the final study visit, the following measurements are taken:
 - Remove study lenses and perform slit lamp assessment to establish anterior segment ocular health.
 - Monocular high contrast visual acuity with sphero-cylindrical refraction (Snellen)
 - If the VA at the Exit Visit is two or more lines worse than at Screening, repeat a monocular sphero-cylindrical refraction (sphere, cylinder and axis) if the best corrected spectacle vision remains two or more lines worse than at Screening, the Investigator will be required to provide an explanation and complete an adverse event form if needed.
 - Post-study follow-up requirement (Y/N). If yes, the reason and date of the follow-visit must also be recorded.
- If the subject is being exited due to discontinuation, further details need to be recorded on the Study Exit Form (App 13).

10 Adverse Events and their Reporting

10.1 Adverse Response Definitions

Adverse Event (AE): An AE refers to any untoward medical occurrence (sign, symptom or disease) in a trial subject that does not necessarily have a causal relationship with the study device. AEs may be classified as 'unanticipated adverse device effects,' 'serious AEs,' 'significant AEs,' or 'non-significant AEs,' as defined below. Adverse events can be ocular or non-ocular.

Classification	Definition
----------------	------------

Serious Adverse Event	Those events that are life-threatening, or result in permanent impairment of a body function, or permanent damage to a body structure or necessitate medical (therapeutic) or surgical intervention to preclude permanent impairment of a body function or permanent damage to a body structure.
Unanticipated Adverse Device Effect	Adverse events in a clinical trial that were not previously identified in the protocol in terms of nature, severity, or degree of incidence. An Unanticipated Serious Adverse Device Effect is an unanticipated adverse event that is serious in nature and caused by or associated with the device and is considered reportable.
Significant Adverse Event	Those non-serious adverse events that occur with contact lens usage that are not sight-threatening but are usually symptomatic and may warrant therapeutic management and /or temporary or permanent discontinuation of contact lens wear.
Non-Significant Adverse Events	Those less severe non-serious adverse events that occur with contact lens usage that are not sight-threatening, may or may not be symptomatic and may warrant palliative management, such as ocular lubricants or temporary interruption of contact lens wear.

AE classification, coding (for reporting to the sponsor) and examples are provided in the following table of Contact Lens Adverse Event Classification and Reporting:

Code	Condition	Potential AE Classification	Reporting
01	Presumed infectious corneal ulcer	SERIOUS	Notify sponsor as soon as possible, within 24 hrs ; IRB reporting as per requirements
02	Permanent loss of ≥ 2 lines of best spectacle corrected visual acuity (BSCVA)	SERIOUS	
03	Corneal injury that results in permanent opacification within central cornea (6mm)	SERIOUS	
04	Neovascularization within the central 6mm of cornea	SERIOUS	
05	Uveitis or Iritis	SERIOUS	
06	Endophthalmitis	SERIOUS	
07	Hyphema	SERIOUS	
08	Hypopyon	SERIOUS	
09	Persistent epithelial defect	SERIOUS	
00	Other serious event	SERIOUS	
11	Peripheral non-infectious ulcer (outside central 6mm)	SIGNIFICANT	Notify sponsor as soon as possible,

12	Symptomatic corneal infiltrative events	SIGNIFICANT	within 5 working days; IRB reporting as per requirements
13	Superior epithelial arcuate lesions (SEALs) involving epithelial split	SIGNIFICANT	
14	Any temporary loss of ≥ 2 lines BSCVA for ≥ 2 wks	SIGNIFICANT	
15	Corneal staining \geq dense coalescent staining up to 2mm in diameter (i.e. moderate staining)	SIGNIFICANT	
16	Corneal neovascularization ≥ 1.0 mm to 1.5mm vessel penetration (if 2 Grade change from baseline)	SIGNIFICANT	
17	Any sign and/or symptom for which subject is administered therapeutic treatment or which necessitates discontinuation of lens wear for ≥ 2 weeks	SIGNIFICANT	
10	Other significant event	SIGNIFICANT	
21	Conjunctivitis: bacterial, viral, allergic	NON-SIGNIFICANT	
22	Papillary conjunctivitis if \geq mild scattered papillae/follicles approximately 1mm in diameter (if 2 Grade change from baseline)	NON-SIGNIFICANT	
25	Asymptomatic corneal infiltrative events	NON-SIGNIFICANT	
26	Localized allergic reaction	NON-SIGNIFICANT	
27	Contact dermatitis	NON-SIGNIFICANT	
28	Any sign and/or symptom for which temporary lens discontinuation for > 1 day is recommended	NON-SIGNIFICANT	
20	Other non-significant sign and/or symptom	NON-SIGNIFICANT	

Normal or adaptive symptoms

Transient symptoms such as end-of-day dryness, lens awareness, itching or burning or other discomfort may occur with contact lens wear and may occasionally reduce wearing time. **These are not reported as adverse events unless they are unexpected in nature, severity or rate of occurrence.**

10.2 Procedures for Adverse Events

Treatment of an adverse event will depend on its nature and severity. Based on the clinical judgment of the investigator the subject may be referred to an ophthalmologist for treatment. The investigator will attempt to determine whether the reaction is related to the study device/procedure or a result of other factors.

An Adverse Event Form will be completed for each adverse event. If both eyes are involved, a separate Adverse Event Form will be completed for each eye. Whenever possible, the adverse event will be photo-documented.

Expenses incurred for medical treatment as part of study participation will be paid by the sponsor (bills and prescription receipts kept). The subject must be followed until resolution and a written report completed indicating the subsequent treatment and resolution of the condition.

10.3 Reporting Adverse Events

All potential **Serious and Unanticipated Adverse Device Effects** that are related or possibly related to subject participation in the investigation will be reported to the Principal Investigator and to the designated medical monitor of the sponsor within 24 hours of the investigator becoming aware of the event (Appendix 2-AE). The Principal Investigator will report the event to the EC/IRB as soon as possible (by fax, mail/delivery, phone, or email), but within 10 business days of becoming aware of the problem. *All fatal or life threatening events will be reported immediately to the IRB.*

Significant and Non-Significant Adverse Events will be reported to the sponsor and the study coordinator as soon as possible, but no later than 5 working days after the occurrence (Appendix 2-AE).

[REDACTED]

[REDACTED]

[REDACTED]

[REDACTED]

[REDACTED]

[REDACTED]

10.4 Discontinuation from the Study

All discontinuations will be fully documented on the appropriate CRF Exit (Appendix 2-EX) and Adverse Event forms (Appendix 2-AE) as needed. Subjects will be followed until resolution and they are free of the study-related complications or other ocular pathology, where possible. When possible, the study lenses involved in an Adverse Event will be returned to the sponsor in a new tightly sealed contact lens case, and labeled with the subject's study ID number and stored in multipurpose solution.

11 Statistical Analysis

11.1 Statistical analysis

Descriptive statistics will be provided on information regarding baseline variables (e.g., age, gender). Differences between lenses and over time will be compared using Paired t-tests. Paired t-tests

/analysis of variance for normal (interval/continuous) data. The appropriate test will be selected based on tests of normality. Means and standard deviations will be provided for each variable.

A Binomial test will be used to analyze the results for the count data of subjective preferences. The number of "no preference" will be evenly distributed to the two options on the basis they would be equally likely to choose either. All subjects who were evaluated will be used in the analysis. In the event of missing data, individual data points will be excluded in the analysis and not extrapolated from the collected data.

12 Data Quality Assurance

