Study Duration	
The anticipated timeline for this study is as follows:
 
 • Subject enrolment begins: Sept 2016 • Last subject visit anticipated: Jan 2017 • Visits: 
V1: Screening & optimize prescription for Avaira toric V2: Dispense new or optimized prescription Avaira Toric - this visit may not be necessary if subjects habitually wear optimized power Avaira Toric V3: Baseline Avaira Toric & Avaira Vitality Toric dispense V4: 2 week follow-up wearing Avaira Vitality Toric V5: 1 month follow-up wearing Avaira Vitality Toric & Exit

Patient Population	Habitual toric contact lens wearers that provide written informed consent and meet protocol entry criteria.
Sample Size	Target enrollment of 48 subjects with the hope of at least 44 subjects being in the analysis cohort.
Study Center Location (US)	USA
Number of Centers	Multi-Center, 4 sites.

Patient Follow-up	
Patients enrolled in this study will be followed up after the each lens dispensing session. Follow-ups at:
 
 ○ at least 1 month lens wear of Avaira Toric ○ 2-week and 1 month wear of Avaira Vitality Toric
Primary Endpoints	
 • Visual acuity with contact lenses, • Lens fit performance (centration, rotation, blink movement) • Investigator's fit acceptability
[REDACTED]	[REDACTED]

Table of Contents

1	Introduction	8
2	Study Objective	8
3	Study Hypothesis	8
3.1	Study Hypothesis.....	8
4	Study Design	9
5	Study Population	9
5.1	Sample Size Calculation.....	9
6	Investigational Sites	9
6.1	Number of Sites.....	9
6.2	Investigator Recruitment.....	9
7	Ethics Review / Statement of Compliance	10
7.1	Relevant Standards / Guidelines	10
7.2	Institutional Review Board	10
7.3	Clinical Trial Registration	10
7.4	Informed Consent.....	10
8	Potential Risks and Benefits to Human Subjects	10
9	Materials and Methods	11
9.1	Subjects.....	11
	Inclusion criteria	11
9.2	Study Materials.....	13
9.2.1	Contact lens.....	13
9.2.2	Contact Lens care.....	13
9.2.3	Rewetting/ lubricating eye drops	13
9.2.4	Storage of Study Medications/Treatments	13
9.2.5	Clinical Supply Inventory.....	14
9.2.6	Disposal of Consumables	14
9.2.7	Masking and Control of Study Materials.....	14
9.2.8	Ordering and Accountability of Study Materials.....	14
9.3	Visit Schedule and Procedures.....	14
9.3.1	Visit 1: Screening visit & Establish Optimum Prescription	15
9.3.2	Visit 2: Dispense of Avaira Toric Lens.....	18

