9.2 Study Materials

9.2.1 Contact lens

All subjects will have worn, or be fit with an optimized prescription in Avaira Toric for at least one month before being fit and dispensed the Avaira Vitality Toric. Details of the contact lenses are shown in Table 1.

The Avaira Vitality Toric lenses will be provided by the Sponsor. The sites may be asked to source the Avaira Toric lenses as needed and retain invoices for reimbursement.

Table1: Study lenses

Brand	Avaira Toric lenses (Control)	Avaira Vitality lenses (Test)
Manufacturer	CooperVision	CooperVision
Material	Enfilcon A	Fanfilcon A
Water Content	46%	55%
Base Curve	8.5	8.4
Lens Diameter	14.5	14.2
Lens Powers Sphere	-1.00 to - 6.00 (0.25 steps)	-1.00 to - 6.00 (0.25 steps)
Lens Power Cylinder	-0.75, -1.25, -1.75	-0.75, -1.25, -1.75
Axis	10 ^o to 180 ^o (10 ^o steps)	10 ^o to 180 ^o (10 ^o steps)
Replacement schedule	Daily wear	Daily wear

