In some circumstances a repeated Dispensing visit (Visit 2R) may need to be scheduled if an over-refraction was found and lenses in a different prescription need to be ordered. The maximum total number of repeat dispense visit permitted will be one (App 2R)

9.3.3 Visit 3: Baseline with Avaira Toric & Dispense of Avaira Vitality Toric lenses

- If subject is an habitual Avaira Toric wearer with optimum prescription then Visit 3 will be scheduled at least 29 days after **Visit 1**
- If subject was fit into new or modified Avaira Toric lenses then Visit 3 will be scheduled at least 29 days after **Visit 2**
- The subject should wear the lenses for a minimum of 2 hours prior to the appointment. If the subject attends without lenses or with less than 2 hours of lens wear on that day and they are not having any problems with their lenses, the visit should be rescheduled, if possible within the visit window. The following clinical test variables will be recorded on the CRFs as indicated:

Visit 3a: Baseline for Avaira Toric Lenses (App 7A)

- Confirm if any changes to health or medications
- [REDACTED]

[REDACTED]

[REDACTED]

[REDACTED]

[REDACTED]

[REDACTED]

- [REDACTED]
- Vision
 - High contrast distance monocular Snellen visual acuity
 - High contrast distance binocular Snellen visual acuity
- [REDACTED]
- Lens fit
 - Lens centration (centered/slightly decentered/substantially decentered)
 - Corneal coverage [Y/N]
 - [REDACTED]
 - Post-blink movement (0-4 Likert scale)
 - [REDACTED]
 - [REDACTED]
 - [REDACTED]
 - [REDACTED]
 - Overall fit acceptance (0 - 4) and reason if Grade 2 or less 1 step.
- Remove study lenses and perform slit lamp examination. A minimum 5 minute washout time after fluorescein insertion is required prior to lens insertion.

Visit 3b: Fitting and Dispensing of Avaira Vitality Toric Lens (App 7B)

The performance of the lenses should be assessed after 10-15 minutes settling time and the following variables will be assessed:

- Record the parameters of the lenses, lot number, and power, on the Dispensing CRF (App 7B).
- Vision
 - High contrast distance monocular Snellen visual acuity
 - High contrast distance binocular Snellen visual acuity
- [REDACTED]
- [REDACTED]
- [REDACTED]
- Lens fit
 - Lens centration (centered/slightly decentered/substantially decentered)
 - Corneal coverage [Y/N]
 - [REDACTED]

– Post-blink movement (0-4 Likert scale)

– [REDACTED]
[REDACTED]
[REDACTED]
[REDACTED]
[REDACTED]

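### Does Section 11.1 need a change because it names no paired test for yes/no corneal coverage?

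*Combined protocol and SAP*

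**What the plan says.** Section 11.1 opens its comparisons with a general statement: "Differences between lenses and over time will be compared using Paired t-tests". A fragment follows that links paired t-tests and "analysis of variance for normal (interval/continuous) data", and then the selection rule: "The appropriate test will be selected based on tests of normality". No test is named for data that fail normality. The only method for counts is limited to preferences: "A Binomial test will be used to analyze the results for the count data of subjective preferences". The section also promises means and standard deviations for every variable.

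The primary outcomes in Section 2 include "Lens fit performance (centration, corneal coverage, post blink movement"). The Protocol Synopsis gives a different list, "Lens fit performance (centration, rotation, blink movement"), with rotation in place of coverage. Coverage is recorded under Visits 3a, 3b and 5 as "Corneal coverage [Y/N"].

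Section 5.1 bases the sample size of 44 on comfort before lens removal. No coverage rate, expected change or power for coverage appears anywhere, and the documents do not say whether coverage is analysed by eye or by subject.

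**The concern.** A yes/no outcome cannot be normal. The within-subject difference takes only the values -1, 0 and 1. With 1 to 15 one-way changes among 44 pairs, five common normality tests all reject (largest p 0.021). Read strictly, the plan's rule steers the analyst away from the t-test and then offers nothing.

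The table could also be sparse and lopsided. Subjects enter only if the study lenses fit acceptably, and Table 1 (row "Lens Diameter") gives 14.2 for the test lens against 14.5 for the control. One might therefore expect a few losses of coverage and almost no gains, which is where the versions of McNemar's test diverge. With 4 losses and no gains the p-value runs from 0.044 to 0.134 depending on the test.

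The stake is interpretive. The study asks whether wearers can be refit with confidence, so a non-significant coverage result could be taken as reassurance. A low-powered test makes that result more likely.

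**Working it through.** **Inputs.** From Section 5.1: 44 analysed subjects, alpha 0.05, power 0.8, SD 2.4, detectable difference 1.04. Two-sided testing is implied by the alternative hypothesis in Section 3.1. Assumed, because the documents are silent: one yes/no pair per subject, and the rates of loss (yes to no) and gain (no to yes).

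**The plan's own figure.** A two-sided paired t-test with 2.4 as the SD of the differences gives a detectable difference of 1.037 at n = 44. The n needed for 1.04 is 43.8, rounded up to 44, and power at 44 is 80.2%. The stated 1.04 reproduces, but it concerns comfort and says nothing about coverage.

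**The candidate tests.** Let b be losses, c gains, m = b + c and n = 44.

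- Uncorrected McNemar: (b - c)²/m on 1 df.
- Continuity-corrected McNemar: (|b - c| - 1)²/m on 1 df.
- Exact McNemar: 2 × P(Bin(m, ½) ≤ min(b, c)).
- Mid-p: the exact p-value minus P(Bin(m, ½) = min(b, c)).
- Paired t on 0/1 scores: d = (b - c)/n, s² = (m - n d²)/(n - 1), t = d/√(s²/n) on 43 df.

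**Worked case, 4 losses and no gains.**

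- Uncorrected: 16/4 = 4.00, p = 0.0455.
- Corrected: 9/4 = 2.25, p = 0.134.
- Exact: 2 × (1/2)⁴ = 0.125.
- Mid-p: 0.125 - 0.0625 = 0.0625.
- Paired t: d = 4/44 = 0.0909, s² = (4 - 0.3636)/43 = 0.0846, t = 2.07, p = 0.0441.

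| Losses v gains | t | Uncorrected | Mid-p | Exact | Corrected |
|---|---|---|---|---|---|
| 3 v 0 | 0.083 | 0.083 | 0.125 | 0.250 | 0.248 |
| 4 v 0 | 0.044 | 0.046 | 0.063 | 0.125 | 0.134 |
| 5 v 0 | 0.024 | 0.025 | 0.031 | 0.063 | 0.074 |
| 6 v 0 | 0.013 | 0.014 | 0.016 | 0.031 | 0.041 |

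**t-test against uncorrected McNemar.** There are 45 × 46/2 = 1,035 possible (b, c) tables at n = 44. The two tests give the same 5% verdict in all of them.

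**Power with losses only.** Losses X follow Bin(44, q). The t-test and uncorrected McNemar reject at X ≥ 4, mid-p at X ≥ 5, and exact and corrected at X ≥ 6. The uncorrected and exact forms therefore disagree when X is 4 or 5. At q = 10% that probability is 0.201 + 0.178 = 0.379.

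| Loss q | t or uncorrected | Mid-p | Exact or corrected | Uncorrected and exact disagree |
|---|---|---|---|---|
| 2% | 0.01 | below 0.01 | below 0.01 | 1% |
| 3% | 0.04 | 0.01 | below 0.01 | 4% |
| 5% | 0.18 | 0.07 | 0.02 | 16% |
| 10% | 0.65 | 0.45 | 0.27 | 38% |
| 15% | 0.91 | 0.81 | 0.66 | 25% |

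**Effect of gains.** At a 10% loss, 1% gains give power 0.47 (uncorrected) and 0.20 (exact), with disagreement in 27% of trials. With 2% gains the figures are 0.33, 0.15 and 19%.

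**Error rates.** Over 1% to 60% discordance the largest type I error is 0.054 uncorrected, 0.047 mid-p and 0.030 exact. None of these forms inflates the error rate materially.

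**The case for a change.** The best argument for a change is that the agreement between the t-test and uncorrected McNemar does not help if the plan's own rule excludes the t-test. The general sentence is followed at once by one tied to normal data and by the normality check, and coverage will fail any such check. The analyst then chooses after seeing the data. The investigators who grade coverage are unmasked, and the result may turn on 4 or 5 subjects. A few added lines would settle the test, the visits compared and the unit, and a confidence interval would guard against overreading a non-significant result: 0 of 44 lost is compatible with up to 8.0%, and 4 of 44 (9.1%) with 2.5% to 21.7%.

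Part of this stands. The section does not explicitly give a paired binary method. The unit is also unstated and moves power more than the test does: treating 88 eyes as independent would give 88% to 98% at a 10% loss, though that ignores the pairing of eyes within a subject. The two primary endpoint lists disagree, so coverage's primary status is itself unsettled; choosing a test does not resolve that.

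The rest is weaker. Unmasked grading may affect the data but has no shown link to test selection. The plan states a two-sided hypothesis of difference and no success rule for coverage. Missing a 10% loss is also partly a matter of sample size, since the most powerful test listed reaches only 65%. Losses without gains are inferred from diameter alone, although Table 1 also shows a different base curve (8.4 against 8.5) and Section 1 describes a changed geometry. Subjects whose test lens fits unsuitably at Visit 3b are discontinued, which may put losses at Visit 5 at the low end of the range.

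**Conclusion.** No change to the plan is called for. The gap is a missing detail that a competent analyst fills in one of two ways. Applying the general t-test sentence gives exactly the verdicts of uncorrected McNemar. Setting it aside leads to a McNemar test, where uncorrected, mid-p and exact are all defensible: the exact form holds its level strictly, and the uncorrected form has more power with a maximum type I error of 0.054. Writing one of them in would record a preference rather than correct an error.

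The size depends on assumptions the documents do not supply: 44 subjects with one value each, no gains, and a loss rate. Disagreement between the uncorrected and exact forms is 1% to 4% of trials at a 2% to 3% loss, 16% at 5% and 38% at 10%. It falls to 19% at a 10% loss once 2% gains are allowed. The 27% to 65% range is therefore an upper illustration, not an expectation. For the graded scales (centration, movement, fit acceptance), t-test and Wilcoxon verdicts differed in under 3% of simulated trials, so nothing follows there either.
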